Only participants who completed the restaurant visit (consumed a meal and completed the questionnaire) will be included in analysis. We will report analyses with any participants who guess the aims of the study included and excluded. We will identify any cases where the height and weight data provided has resulted in an implausible BMI value (<12kg/m² and >100kg/m²(49)) and exclude these subjects from analysis involving BMI.

Participant characteristics will be presented in a table. Data will include age, gender, ethnicity, BMI and highest education level. Continuous variables will be summarised by means and standard deviations, categorical variables will be summarised by counts and percentages. The descriptives table will report variables overall and split by condition and outlet.

Descriptive analyses:

We will report quantitative questionnaire findings and main outcomes by condition in a table. This will consist of: frequency of eating OOH food, health food choice motive scores, label awareness/understanding, PME, UK NPM score, kcal selected and consumed and the proportion of participants selecting food with each label (A-E). As above, these variables will be reported overall and split by condition and restaurant.

Anticipated primary analyses:

Shortly after starting data collection and prior to any interim analyses, we will finalise the full analysis plan and publish this alongside the protocol on the Open Science Framework. The anticipated analysis approach is briefly stated below.

PME

A linear mixed model will be used to assess the impact of labelling condition (calorie labelling only/NS with calorie labelling) on PME relating to the food menu (a mean score).

Nutritional quality of ordered meal (UK NPM score)

A further Linear mixed model will be conducted to explore the impact of labelling condition (calorie labelling only/NS with calorie labelling) on the nutritional quality of the participant's full meal (mean weighted UK NPM score: linear outcome variable).

Secondary analyses:

Likelihood of selecting a healthier option (A/B)

Any participants who have selected a healthier item (A/B) as part of their meal will be coded as 1 and participants who have only selected options with a C/D/E value will be coded as 0. We will conduct a logistic regression to test whether NS labelling (Y/N) is associated with the likelihood of selecting a healthier item.

Likelihood of selecting a less healthy option (D/E)

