Similar to the above, any participants who select a less healthy item (D/E) as part of their meal will be coded as 1, and participants who have only selected options with a A/B/C value will be coded as 0. We will conduct a logistic regression to test whether NS labelling (Y/N) is associated with the likelihood of selecting a less healthy item.

Energy and nutrient content consumed at lunch

Similar to primary analyses, we will explore the impact of NS labelling on total energy and nutrient content of food consumed (linear outcome variables) through n=8 linear mixed models. The nutrients explored will be salt, sugar, fat, saturated fat, protein, fibre and fruit vegetable and nut content.

Transformations: N/A

Inference criteria: Results for primary analyses will be considered significant at p<0.05, and to account for multiple comparisons, secondary analyses will be considered significant at p<0.01.

Data exclusion: If participants leave the restaurant study session without ordering food their data will be excluded from analyses.

Missing data: If participants do not complete the dietary recall survey, and therefore do not provide data of later intake, then we will impute the missing data for this variable. Any missing data for other outcomes (e.g., PME) will also be imputed. We will complete multiple imputation with 5 imputed datasets(50) in R using the 'mice' package. Imputation will be reported in line with published guidance(51).

Exploratory analysis:

Other:

Sample size:

We conducted a simulation to estimate sample size required for two primary outcomes: PME and NPM scores. Our simulation was based on previous research and knowledge of the outlets confirmed for data collection.

We simulated running the study with 20 participants a day for 20 days (400 total data points). For PME, we estimated from previous research that we may have an intercept PME value of 1.85 (SD: 1.08), with an intervention effect of 1 (the intervention group will have PME values 1 unit greater than the control group on average, based on previous research(52)), and minimal difference in PME

scores between the two outlets (0.2). We also assumed ICC of approximately 0.200, and a standard deviation of the random intercept of eating group in a mixed model of 1. Across 200 simulations using a regression model clustered by day, we would have 94% power (95% CI 89.75, 96.86) to detect differences in PME between the two conditions.

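### Two primary outcomes are each judged at p<0.05 with no rule linking them, and the 0.01 level said to cover the secondary comparisons is the Bonferroni level for five tests, not the ten listed

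*Protocol*

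**What the plan says.** **Levels.** Inference criteria fixes two thresholds: "Results for primary analyses will be considered significant at p<0.05, and to account for multiple comparisons, secondary analyses will be considered significant at p<0.01". It names no family-wise target and does not derive the 0.01.

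**Primary outcomes.** Sample size refers to "two primary outcomes: PME and NPM scores" and powers each separately. Anticipated primary analyses lists a mixed model for PME and then NPM ("A further Linear mixed model will be conducted to explore the impact of labelling condition"). The closing paragraph of the introduction ranks them differently: PME is the main objective and NPM is among the secondary objectives.

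**Secondary tests.** Secondary analyses lists one logistic regression for choosing an A/B item ("We will conduct a logistic regression to test whether NS labelling (Y/N) is associated with the likelihood of selecting a healthier item"), a second for choosing a D/E item, and energy and nutrients consumed, analysed "through n=8 linear mixed models".

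**Interim.** Stopping rule examines both primary outcomes at about half the sample (224 of 450). If recruitment continues, it applies a factor of 2 at the final analysis to the outcomes already examined, to allow for the repeated analysis.

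**The concern.** With two primary outcomes judged separately, a reader will take a significant result on either as a positive trial unless the plan says otherwise. The plan gives no hierarchy, no division of alpha and no rule that both must succeed. The only other adjustment, in the Stopping rule, has a different purpose.

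For the secondary analyses, the plan says that the threshold deals with multiplicity. If it does not hold the family error at a conventional level for the tests listed, a result at, say, p = 0.008 would be reported as having survived a correction when control was never established.

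**Working it through.** **Inputs.** From the protocol: 0.05 per primary analysis; 0.01 per secondary analysis; two primary outcomes; secondary tests = 2 logistic regressions + 8 mixed models (energy + 7 nutrients) = 10; interim at about half the sample; factor of 2 at the final analysis. Assumptions: two-sided tests, a 5% family-wise target, and the correlations. The protocol states none of these.

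**1. What 0.01 corresponds to.** Bonferroni level = 0.05/k.
- k = 5: 0.05/5 = 0.01, the plan's figure.
- k = 8: 0.05/8 = 0.00625.
- k = 10: 0.05/10 = 0.005.

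**2. Secondary family, ten tests at 0.01.** If independent, 1 − 0.99^10 = 0.0956. With equally correlated normal statistics (simulation, 400,000 draws):

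| Common correlation | Chance of at least one false finding |
|---|---|
| 0 | 9.6% |
| 0.3 | 8.7% |
| 0.5 | 7.3% |
| 0.7 | 5.4% |
| 0.9 | 3.1% |

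At 0.005 per test and independence, 1 − 0.995^10 = 4.9%.

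**3. Two primaries at 0.05, single look.** If independent, 1 − 0.95² = 0.0975. At correlation 0.5 the simulated value is about 9.1%.

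**4. Two primaries with the interim.** Taken literally, dividing a p value by 2 makes the test looser. I read the factor as a halved final level, 0.05/2 = 0.025. With equal halves of information and independent outcomes (simulation, 1,000,000 draws):

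| Efficacy claim at interim | Final level | Error per outcome | Error for either outcome |
|---|---|---|---|
| none possible | 0.025 | 2.5% | 5.0% |
| at 0.025 | 0.025 | 4.3% | 8.4% |
| at 0.05 | 0.025 | 6.5% | 12.5% |

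The last column follows from the one before: 1 − (1 − 0.065)² ≈ 12.5%, for example.

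**5. If the objectives' ranking is taken.** With PME as sole primary, the two-outcome inflation disappears. NPM becomes an eleventh secondary test: 1 − 0.99^11 = 10.5% at 0.01 if independent.

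**6. Cost of splitting alpha.** One reconstruction gives about the stated 94% PME power: tables of 4 (assumed), 50 tables per arm, random-intercept variance 1, and residual variance (1 − 0.2)/0.2 = 4. Then SE = √(2 × (1 + 4/4)/50) = 0.283 and effect/SE = 1/0.283 = 3.54. Power is Φ(3.54 − 1.96) ≈ 94% at 0.05 and Φ(3.54 − 2.24) ≈ 90% at 0.025.

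**The case against.** **The primaries are not left wholly uncorrected.** A reader might infer from Inference criteria alone that 9.75% is this design's error rate. The documents do not support that: the factor of 2 applies to the two primary outcomes if the study continues, and 9.75% is a single-look figure. What stands is that the factor is there for the repeated look, and that it covers both sources of error only if the interim cannot yield an efficacy claim. The Stopping rule does not say this. It describes the interim as judging whether the evidence is strong enough to conclude that effects exist.

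**The sentence does not claim to correct the primaries.** This is right. The reference to multiple comparisons attaches to the secondary analyses only. On the primary side the defect is a missing rule, not a false statement, and it matters only if either outcome alone can carry a claim. The plan does not settle that.

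**The introduction makes NPM secondary.** On that reading the primary half falls away. But Anticipated primary analyses, Sample size and Stopping rule all treat NPM as primary, so the result is a conflict of roles and not a resolution.

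**Fitting five tests is an inference.** Also right: the plan names neither Bonferroni nor a 5% target. Energy and nutrients consumed are computed from the same items and the same proportions eaten, so substantial correlation is plausible, and a flat statement that the secondary error exceeds 5% would be too strong. It remains true that the plan gives no basis for 0.01 over ten tests, two of which concern item selection and not intake.

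**Later intake.** A reader might add the later-intake variables to the count. No test of them is listed, so they are left out.

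**Deferral.** A fuller analysis plan is promised before any interim analysis, and detailed procedures may sit there. The protocol nevertheless fixes the two levels and makes the claim about them.

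**Conclusion.** The point holds in two parts.

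- **Primary.** Two outcomes are each judged at 0.05 with no rule linking them, and their roles differ between the objectives and the analysis sections. If either can support a claim, the false-positive chance is up to 9.75% at a single look. With the halved final level it ranges from about 5% to 12.5%, depending on an interim efficacy rule that the plan does not state. These figures assume independent outcomes and two-sided tests.
- **Secondary.** The statement that 0.01 accounts for the comparisons is not supported for the ten tests listed. Against an assumed 5% target the excess is moderate: 9.6% if independent, near the target at correlation 0.7, and gone at 0.9.

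The design and the sample size are not called into question by this point.

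**What to change.** 1. **Primary outcomes.** State that PME is tested first and that NPM is confirmatory only if PME is significant, both at the level that remains after the interim adjustment. Make the objectives agree with the primary-analysis, sample-size and stopping-rule sections. State whether an efficacy claim is possible at interim and at what level, because the fixed order does not repair that: with the interim at 0.05 and the final at 0.025, PME alone still carries 6.5%. The order follows the protocol's own main objective and costs PME no power, whereas an even split would take it from about 94% to about 90%. The cost is that NPM is not confirmatory if PME fails.

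2. **Secondary outcomes.** Either replace the flat 0.01 with Holm's procedure at 5% over the ten listed tests, or stop saying that 0.01 accounts for the comparisons and report these tests as exploratory. Under Holm the smallest p value must be at most 0.05/10 = 0.005. The limit then rises step by step, reaching 0.05/5 = 0.01 at the sixth smallest. If NPM is made secondary instead, the family is eleven and the first limit is 0.05/11 = 0.0045.

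The changes are a few sentences in the objectives, Inference criteria and Stopping rule, and should be made before the interim data are examined.

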Study design: Businesses are being actively recruited for this study. We aim to have a minimum of two outlets available for participants to visit. This study is a randomised controlled trial using a between-subjects design. Participants will be asked to visit a restaurant to eat lunch and complete some questionnaires. Participants will select one of the available restaurants to visit and will be randomly assigned to one of two conditions: Calorie labelling only or NS with calorie labelling. Later intake (over the rest of the day, after the lunch time study session) will be self-reported by participants. If one outlet is more popular than the other outlet(s), and we are not obtaining a similar number of participants for the outlets on offer, then we will actively recruit participants to each of the outlets to ensure a similar number of participants are recruited to each outlet tested.

Randomisation: Participants will be randomised to one of the two conditions. Data collection days at each of the outlets will be randomised as either NS with calorie labelling or calorie labelling only. Data collection days will be randomly assigned to condition using the RANDBETWEEN function in excel.

Sampling Plan

Existing Data: Registration prior to creation of data

Explanation of existing data: N/A

Sample

Data collection procedures: We will use an existing participant database consisting of local volunteer participants recruited through social media advertising. Only participants who have not taken part in previous similar research conducted by the appetite group at the University of Liverpool will be contacted. If required, more participants will be recruited from the local community (e.g. adverts on social media/posters in the university). Participants who sign up to the study can bring up to 4 guests with them to also take part. Tables of 5 participants were determined as the upper limit as it was deemed a manageable size for researchers to effectively monitor individual orders. Over the course of the study, we will attempt to ensure our sample is representative of the UK population in terms of gender (50% male, 50% female), age (36% aged 18-39; 64% aged 40+(31)), and SEP - education level (50% level 3 and above (2+ A-levels or equivalent, not including apprenticeships(32)).

Inclusion criteria:

- Can visit a restaurant in Liverpool city centre
- Regularly eat food prepared out of the home (from restaurants, cafes, fast food etc., at least once a month)

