For NPM scores, we calculated using the two confirmed outlet menus, that we may have an intercept NPM score of -0.27 (SD: 3.29) with an intervention effect of 0.22 (the intervention group will select meals with with greater nutritional quality, shown by a 0.22 higher NPM score) based on previous research(26) and a mean difference between the two outlets of 1.4 (the difference in mean NPM scores for the two outlets). We also assumed ICC of approximately 0.819, and a standard deviation of the random intercept of eating group in a mixed model of 1. Across 200 simulations using a regression model clustered by day we would have 88.5% power (95% CI 83.25, 92.57) to detect differences in NPM scores between the two conditions.

Due to uncertainty over size of anticipated effects and available resources, we will increase the above desired maximum sample size (400) by 12.5% to 450 participants.

Stopping rule

Prior to the study we do not know with certainty what the rate of participant recruitment will be, and effect size estimates have a degree of uncertainty. To balance the trade-off between costs (e.g., in research time, participant burden) and likelihood of the study providing convincing evidence, we will conduct interim analyses to assess whether the results are convincing enough to conclude that effects on PME and nutritional quality of food order are present(53). The interim analyses will examine the effect sizes of these two primary outcomes and observed statistical significance. We will also calculate Bayes Factors to assess the strength of evidence for the experimental vs null hypotheses.

We will conduct the interim analysis when we have obtained approximately 50% of the full sample (224 participants, ~112 completers in each condition). If at this point, the data suggests that it is extremely unlikely that either of the predicted effects would be observed up to maximum sample size capacity (described above), and if Bayes Factors suggest there is evidence for the null hypothesis (BF10 < 0.3) then we will cease data collection and conduct full planned analyses.

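### Five imputed datasets is too few: later-intake results would depend avoidably on the random seed, and at least 50 would remove most of this at almost no cost

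*Protocol*

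**What the plan says.** The Missing data paragraph of the protocol's Analysis Plan addresses later intake first. For anyone who skips the next-day recall, the rule is: "then we will impute the missing data for this variable". The rule is not confined to the recall, since a further sentence reads: "Any missing data for other outcomes (e.g., PME) will also be imputed". The number of datasets is fixed: "We will complete multiple imputation with 5 imputed datasets". For software, the paragraph names only the R package mice. Five is not tied to an expected missing rate or to any reproducibility target. The imputation method, the predictors and the handling of clustering are not stated.

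Under Randomisation, the allocated unit is the day: "Data collection days at each of the outlets will be randomised as either NS with calorie labelling or calorie labelling only". The Sample size section uses a day-clustered layout: "We simulated running the study with 20 participants a day for 20 days (400 total data points". It then raises the target: "we will increase the above desired maximum sample size (400) by 12.5% to 450 participants". It assumes an ICC of about 0.200 for PME and gives none for later intake. The section on anticipated primary analyses describes the approach as brief and promises a full analysis plan before any interim analysis.

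**The concern.** Later intake is the variable most exposed to missing data, because it is collected by email after the participant has left the restaurant. It also carries the compensation question, which the protocol's introduction names as a gap in existing research. All missing values are to be filled by multiple imputation.

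With a small number of datasets, m, the pooled estimate and its standard error both vary from one run to the next on the same data. The between-imputation variance is then estimated from five values, on four degrees of freedom. The Inference criteria paragraph uses fixed thresholds of 0.05 and 0.01. A result near such a line could be called significant under one seed and not under another. That arbitrariness is avoidable.

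A second matter depends on a choice not yet disclosed. When days are randomised, between-day variation drives the standard error of the arm comparison, so it matters whether the imputation model includes day.

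**Working it through.** **Inputs from the protocol.** m = 5; 20 participants per day; days as the randomised unit; ICC about 0.200 for PME. There is no derived figure behind m = 5 to reproduce.

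**Assumptions.** The documents give neither a missing rate nor an ICC for later intake. I take 30% missing recalls, so 14 of 20 are observed per day, and an ICC between 0 and 0.20.

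**Step 1: fraction of missing information (FMI).** The variance of a day mean is proportional to ICC + (1 − ICC)/n. With day in the imputation model, approximately

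FMI = 1 − [ICC + (1 − ICC)/20] / [ICC + (1 − ICC)/14]

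- ICC 0.20: 1 − 0.2400/0.2571 = 0.07
- ICC 0.05: 1 − 0.0975/0.1179 = 0.17
- ICC 0: 1 − 14/20 = 0.30

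The plausible range at 30% missing is therefore about 7% to 30%.

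**Step 2: Monte Carlo error of the pooled effect**, as a share of its standard error, is about √(FMI/m).

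| FMI | m = 5 | m = 50 |
|---|---|---|
| 0.07 | √0.0140 = 0.12 | √0.0014 = 0.04 |
| 0.17 | √0.0340 = 0.18 | √0.0034 = 0.06 |
| 0.30 | √0.0600 = 0.24 | √0.0060 = 0.08 |

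**Step 3: spread of the p-value across seeds.** Take one data set whose result with unlimited imputations would be z = 2.2 (p about 0.03). Within-imputation variance is 1 − FMI and between-imputation variance is FMI. Simulate the pooled estimate and the estimated between-imputation variance, then apply Rubin's rules with the classical degrees of freedom. The 5th to 95th percentiles of the p-value are:

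| FMI | m = 5 | m = 50 |
|---|---|---|
| 0.07 | 0.016 to 0.050 | 0.024 to 0.033 |
| 0.17 | 0.011 to 0.080 | 0.021 to 0.038 |
| 0.30 | 0.007 to 0.12 | 0.018 to 0.043 |

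**Step 4: does a small m shrink standard errors?** No. Rubin's total variance contains the factor (1 + 1/m), which carries the extra noise. The expected inflation is √(1 + FMI/m) − 1. At FMI 0.30 that is 3.0% with m = 5 and 0.3% with m = 50. In null simulations of day-randomised trials with an ICC of 0, the ratio of model to true standard error at m = 5 was 0.99 to 1.01.

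**Step 5: conditional check, if day were left out of the imputation model.** Null trials of 20 to 22 days with 20 people each were simulated (450/20 = 22.5 days). Imputation was single-level normal with arm but no day term, followed by a day-level analysis and Rubin's rules, with m = 5.

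| Day ICC | Missing | Model SE / true SE | Type I error at nominal 5% |
|---|---|---|---|
| 0.20 | 20–40% | about 0.75 to 0.85 | about 8% to 11% |
| 0.05 | 20–40% | about 0.87 to 0.90 | about 5% to 6% |

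At ICC 0.02 the inflation was negligible. Raising m does not repair this: at ICC 0.20 and 30% missing, the ratio was 0.78 with m = 5 and 0.84 with m = 50, both well below 1. Entering day as a fixed factor overcorrects: the ratio was 1.17 at ICC 0.05, 30% missing and m = 5. A random day intercept matches the design but was not simulated.

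**The case against.** The strongest reply is that little in the text turns on this. Later intake is measured, but no model or test for it appears among the primary or secondary analyses, so no specified p-value is at risk. Efficiency at m = 5 is respectable: the standard error grows by at most about 3% at the assumed FMI. If outcomes cluster strongly by day, FMI falls to about 7% and the seed matters less. PME should have few gaps, since only participants who completed the questionnaire are analysed, and lunch outcomes come from orders and photographs. All of this stands and keeps the point small. It does not defend the number five, which the protocol fixes and which costs nothing to raise.

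A reader might go further and infer that the planned imputation ignores the randomised days, so that later-intake standard errors will be too small. The documents do not support that. They name only the package, which also offers two-level methods. Silence on the imputation model is not an error, because such detail commonly belongs in the analysis plan, and one is promised. Nor does m = 5 itself shrink standard errors (Step 4).

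**Conclusion.** The point holds as a minor one. Five imputations leave avoidable seed noise of about 0.12 to 0.24 of a standard error, enough to move a p-value near 0.03 to either side of 0.05 when missing information is 17% or more. At 7% the range only just reaches 0.05. These sizes rest on an assumed 30% of recalls missing and an assumed ICC of 0 to 0.20 for later intake; the documents give neither figure.

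The day point is conditional advice for the full analysis plan. It would matter only if day were omitted and the outcome's ICC were near 0.20, which is the protocol's assumption for PME and not for later intake. At an ICC of 0.05 or below the effect on type I error is slight. The 20–40% missing used in that check suits the recall and should not be carried over to PME.

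**What to change.** In the Missing data paragraph, replace 5 with at least 50 imputed datasets, and fix and record the seed. The seed makes the result repeatable; the larger m is what reduces the noise. The cost is computing time only.

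When the full analysis plan is finalised, state the imputation model: a two-level method in mice with a random day intercept, and with arm and outlet as predictors. Day should not be entered as a fixed factor. This takes a few lines of code. The two changes are separate, and neither substitutes for the other.

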Only one study has explored how NS impacted food choices in a work cafeteria(26). This study used a non-randomised design with no control group and found introduction of NS was associated with improved nutritional quality of food choices (UK NPM score -0.22; 11.5%), and lower selected energy content. However, due to data being gathered through receipts, this study did not collect information on consumption or demographic characteristics, so individual differences in impact of NS could not be explored. The impact of NS labels in a full-service restaurant setting has not yet been tested. Recent research has considered the role of expectations in determining the potential impact of NS labels(27). This study found that due to underlying expectations of healthiness, effectiveness of NS may be reduced. For example, if a product was anticipated to be the least unhealthy category ('E') but was rated healthier (e.g. 'D'), there may be increased selection of the product marked 'D' due to reduced guilt around eating the product. Therefore, labelling combined with expectations may result in less healthy food selection. Due to this uncertainty surrounding NS labelling, it is important we test the effectiveness of NS in the OOH food sector.

There have been a small number of cross-country studies assessing various food labels on consumer understanding and choice that have included UK participants(28, 29), and one online study of UK participants exploring the impact of labelling types on the ability of participants to rank packaged food items in order of healthiness(30). However, there is no research we are aware of that has tested NS labels on food choice in a UK OOH context.

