An adapted version of the University of North Carolina PME scale(38) will be used to measure health concern, product attitude, and discouragement of item consumption in response to the food menu. Participants will be given the menu they ordered from to look at. All participants will answer 3 questions using a Likert scale ranging from 1 - 5 anchored by "not at all" and "a great deal". The mean response to the three items will be calculated. PME is used as an early indicator of a health message's potential to change behaviour (e.g., reduce selection of less healthy items)(17). The scale has been used previously to identify the potential impact of food labels and is predictive of long-term behaviour (39-45).

NS label of each item selected (A,B,C,D,E).

A NS category value will be recorded for each item selected by participants.

Nutritional quality of each item and for the full meal

Nutritional quality for meal choices will be calculated using the UK NPM scoring system(46). This calculates a score (continuous variable) for a product by deducting a total score for positive nutrients from a total score for negative nutrients. A lower score represents greater nutritional quality and a higher score represents poorer nutritional quality.

We will calculate the mean NPM score weighted by energy content of items for each participant. This will ensure that the NPM score of main dishes will be weighted higher than that of starters or sides (assuming energy content of selected main is higher than any starters or sides), leading to a more representative overall NPM score for food orders. This will be done using the weighted.mean function in R(47). This function multiplies each value (i.e. NPM scores for individual items) by its corresponding weight (kcal content of individual items), sums all items and then divides this by the sum of the weights.

Energy content of all food ordered

The sum of energy (kcal) across all foods ordered for the meal will be calculated

Energy and nutrients consumed

Researchers will take pictures of plates before and after each item is given to participants. Researchers will estimate the percentage of each dish consumed, by estimating the percentage of individual meal components that have been eaten. Estimations will be guided by the information available from the nutritional analysis of items, which details the proportion of the meal that is made up by individual components. For example:

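### The 88.5% power stated for the NPM outcome does not follow from its inputs: at SD 3.29 it is about 10% or less, and the effect has the wrong sign

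*Protocol*

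**What the plan says.** The Sample size section of the protocol names PME and NPM as the two primary outcomes and simulates 20 days of 20 participants, 400 in all. For NPM it states: "we may have an intercept NPM score of -0.27 (SD: 3.29) with an intervention effect of 0.22". It adds an outlet difference of 1.4 and continues: "We also assumed ICC of approximately 0.819, and a standard deviation of the random intercept of eating group in a mixed model of 1". From 200 simulations, analysed by a regression clustered by day, it concludes: "we would have 88.5% power (95% CI 83.25, 92.57) to detect differences in NPM scores between the two conditions". The maximum is then raised from 400 to 450.

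The expected benefit is worded as follows: "the intervention group will select meals with with greater nutritional quality, shown by a 0.22 higher NPM score". Under Measured variables the scale is defined the other way: "A lower score represents greater nutritional quality and a higher score represents poorer nutritional quality". The introduction reports the cafeteria study from which the 0.22 is taken as a change of -0.22, described as an improvement.

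The Randomisation and Procedure sections assign whole data collection days to one menu or the other.

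**The concern.** The planned effect is a very small fraction of the stated SD, so power near 90% from 400 people is implausible before clustering is considered. Because condition is fixed for a whole day, it never varies within a day or a table, and positive correlation within either can only reduce power.

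NPM is one of the two outcomes used to set the sample size. It is also one of the two examined at the interim analysis, where the Stopping rule refers to the predicted effects and to an effect detectable at 450. If the stated power is accepted, a null NPM result may be read as coming from a well-powered test when the design can hardly see the planned effect. The reversed sign leaves the predicted direction of a primary outcome contradictory within the protocol.

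**Working it through.** **Inputs** (Sample size section unless noted): N = 400; effect 0.22; SD 3.29; ICC 0.819; group-intercept SD 1; alpha 0.05 (Inference criteria; sidedness is not stated, two-sided assumed). Table size is not given. The protocol caps tables at five, so I show tables of 2, 4 and 5, and whole days of 20.

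**1. The printed interval.** 88.5% of 200 is 177. The exact binomial 95% interval for 177/200 is 83.25% to 92.57%, as printed. It describes simulation noise only and says nothing about whether the simulated model matches the inputs.

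**2. No clustering, SD 3.29.**
- SE = 2 × 3.29 / √400 = 0.329, and 0.22 / 0.329 = 0.67.
- Two-sided power is 10.3%; one-sided it is 16.4%.
- At N = 450, SE = 2 × 3.29 / √450 = 0.310 and two-sided power is 10.9%.

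**3. Consistency of the variance inputs.**
- Group SD 1 with ICC 0.819: residual variance = 1 × (1 − 0.819) / 0.819 = 0.221, so residual SD 0.47 and total SD √1.221 = 1.10, not 3.29.
- Group SD 1 with residual SD 3.29: ICC = 1 / (1 + 10.82) = 0.085, not 0.819.

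**4. Power at N = 400 under each reading.** SE = 2 × √(between × m/N + within/N), with m people per cluster; normal approximation, two-sided.

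| Reading | Independent | m = 2 | m = 4 | m = 5 | m = 20 (day) |
|---|---|---|---|---|---|
| Total SD 3.29, ICC 0.819 | 10.3% | 7.9% | 6.5% | 6.2% | 5.3% |
| Group SD 1, residual SD 3.29 | 9.8% | 9.4% | 8.8% | 8.6% | 6.8% |
| Total SD 3.29, group SD 1 | 10.3% | 9.8% | 9.1% | 8.8% | 6.9% |
| Group SD 1, residual SD 0.47 (3.29 dropped) | 51% | 31% | 19% | 16% | 7.8% |

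Simulating 20 days of 20 people, with day-level assignment, an outlet difference of 1.4 and day-clustered standard errors, agrees. It gives 10 to 32% for the last row with clustering and about 6 to 9% for the clustered scenarios simulated at SD 3.29.

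**5. What 88.5% would need.** The multiplier is 1.960 + 1.200 = 3.160. Without clustering:
- at N = 400, an SD of 0.22 × √400 / (2 × 3.160) = 0.70; or
- at SD 3.29, N = (2 × 3.29 × 3.160 / 0.22)² ≈ 8,900.

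**6. Detectable difference at N = 450, 80% power, SD 3.29.** 2.80 × 0.310 = 0.87 without clustering. With tables of 4, multiply by √(1 + 3 × ICC): 1.1 at ICC 0.2 (the value the protocol uses for PME) and 1.6 at ICC 0.819.

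**7. Comparison with PME.** The 94% for PME can be matched with group SD 1, ICC 0.2 and tables of 4 (94.2%). The same construction gives 19% for NPM. The match uses a residual SD of 2 (variance 1 × 0.8 / 0.2 = 4), which does not sit with the PME SD of 1.08 either.

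**8. Sign.** The Sample size section equates better quality with a higher score. Measured variables and the introduction both make better quality a lower score. Two-sided power is the same for +0.22 and -0.22, so this does not explain the discrepancy.

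**The case against.** The inputs were calculated from the outlet menus, so 3.29 may be the spread across menu items. The outcome is an energy-weighted mean per participant and could vary less. The document does not settle which SD is right, so a replacement figure of 10% should not be presented as certain. That stands: the 10% is conditional on SD 3.29. It does not rescue 88.5%, because the reading that drops 3.29 and keeps the group SD and ICC still reaches only 51% with everyone independent.

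Higher figures can be produced. A contrast within clusters at residual SD 0.47 gives 99.7%, but day-level assignment rules it out. An ordinary regression that ignores day clustering rejects up to about 70% of the time, but also about 63% of the time when there is no effect.

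The sign is a slip in one parenthesis. The same sentence speaks of better quality, and the Hypotheses section has the direction right. The interim rule uses observed effects, significance and Bayes factors, and neither 88.5% nor 0.22 is a threshold in it. Both points are fair and make the sign and the interim consequence secondary. The wording still contradicts the scale, and the rule does refer to predicted effects.

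Finally, the introduction makes PME the main objective and lists NPM as secondary. The error therefore does not undermine the PME objective. The Sample size and analysis sections nevertheless treat NPM as primary and attach this power to it.

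**Conclusion.** The concern holds. The stated 88.5% is not obtainable from the stated inputs under day-level assignment. At SD 3.29 and two-sided 5%, power for 0.22 is 10.3% at 400 and 10.9% at 450 without clustering, and about 5 to 10% at 400 with it. With 3.29 set aside it is 8 to 31% with clustering and 51% without. Table size and a two-sided test are assumptions; a one-sided unclustered test at SD 3.29 gives 16%. The three variance inputs cannot all be true, and the direction of the effect is reversed.

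The cause cannot be established without the simulation code. One possibility is that the wrong coefficient was read: power for the 1.4 outlet difference, with day as the cluster, group SD 1 and residual SD 0.47, is about 83 to 88%.

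**What to change.** - Check the simulation code, including which coefficient was tested.
- Decide what 3.29 describes, and state one coherent set: a participant-level total SD, split by the ICC into between and within parts, with the clustering level (table, day or both) named. If 3.29 is the participant-level SD, that is the total to split.
- Rerun with whole days assigned to condition and an effect of -0.22.
- Replace 88.5% with the result (about 10% or less if SD 3.29 stands). State the detectable NPM difference at 450 with its assumptions: 0.87 is the floor without clustering, and 1.6 applies with tables of 4 at ICC 0.819.
- Rest the sample-size justification on PME, reconciling its SD, ICC and group SD in the same rerun.
- Change higher to lower in the description of the NPM effect.

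The cost is one rerun and a reworded section. No participants are added and the study procedures do not change. The price is an openly low power for NPM, so a null NPM result should be reported with its confidence interval and not as evidence of no effect.
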